Appendix 1: Draft questions for the email survey:

1. Do you take care of patients who receive stent(s) and are taking clopidogrel therapy? O Yes O No (Can stop questionnaire)
2. What is your current position? O Resident/Fellow physician O Other type of physician O Inpatient Pharmacist O Nurse O Outpatient Pharmacist O Physician Assistant O Cardiologist O Nurse Practitioner O Hospitalist
3. Who is primarily responsible for prescribing clopidogrel at your facility at hospital discharge? (check all that apply) O Resident/Fellow physician O Other type of physician O Inpatient Pharmacist O Nurse O Outpatient Pharmacist O Physician Assistant O Cardiologist O Nurse Practitioner O Hospitalist
4. How often do you estimate that pharmacists bring the patient's discharge medications to the bedside at your facility? O All of the time (100%) O Infrequently (10-39%) O Most of the time (70-99%) O Almost never (1-9%) O Some of the time (40-69%) O Never (0%)
5. If not all of the time, why is this not the usual practice in your opinion? (Free text comment)
6. Do you think it is feasible to have clopidogrel brought to the patient's bedside prior to hospital discharge? O Yes O No If yes, who would be in the best position to do this? If no, what are the barriers that make this not feasible?
7. Who is primarily responsible for prescribing clopidogrel at your facility in the outpatient setting? (check all that apply) O Resident/Fellow physician O Other type of physician O Inpatient Pharmacist O Nurse O Outpatient Pharmacist O Physician Assistant O Cardiologist O Nurse Practitioner

 Hospitalist  Primary care physician

8. Does your site have a program (e.g. pharmacist follow-up) to facilitate or ensure adherence to clopidogrel in the outpatient setting?
 
 Yes  No
 
If yes, please describe the program.
 
(Free text comment)

9. What happens if patients delay or do not refill their clopidogrel as an outpatient? Please describe.
 
(Free text comment)

10. Do you think it would be helpful to notify a provider when a patient has not refilled their clopidogrel?
 
 Yes  No
 
If yes, who would be the best person to notify?
 
(Free text comment)


11. In your opinion, is it feasible for providers to contact the patient to assess and ensure patients refill their clopidogrel?
 
 Yes  No
 
If no, what are the potential barriers?
 
(Free text comment)
 
If yes, who would be the best person to do that at your facility?

12. Do you think an automated telephone call reminding patients to refill their clopidogrel would be helpful?
 
 Yes  No
 
If no, what would be other alternatives to remind patients to refill their clopidogrel?
 
(Free text comment)

13. Would you be willing to lead implementation of a multi-faceted intervention to improve clopidogrel adherence at your site?
 
 Yes  No

If no, who would you recommend?

Appendix 2: Key informant interviews for baseline assessment of clopidogrel adherence programs

1. Introduce self:

Hello, my name is [name of interviewer]. I am working on the Hybrid Effectiveness-Implementation Clopidogrel Study. [Name of person who set up interviews] contacted you [when: e.g., a few weeks ago] to set up this interview appointment.

2. Introduce the project:

- The Hybrid Effectiveness-Implementation Clopidogrel Study is a study to test an intervention to improve clopidogrel adherence among patients who undergo percutaneous coronary intervention (PCI).
- We are evaluating a multi-faceted intervention comprising of automated alerts that will remind pharmacists to come to the bedside of PCI patients to educate them and ensure they are discharged with clopidogrel, and interactive voice response (IVR) follow-up telephone calls with patients to refill clopidogrel. The goals of the study are to test the effectiveness of the intervention in improving clopidogrel adherence and reducing adverse outcomes, and to understand how to best implement the intervention in VA facilities.
- The intervention consists of 4 components:
 - A reminder from CART-CL will be sent to the inpatient pharmacist prior to discharge that a patient has received a stent;
 - The pharmacist will educate the patients on the importance of and adherence to clopidogrel following PCI, as well as bring clopidogrel to the patient's bedside prior to hospital discharge;
 - Interactive voice response (IVR) calls will be made to patients prior to the time of clopidogrel refill to remind patients and to facilitate refills during follow-up; and
 - A Patient Aligned Care Team (PACT) member will contact patients who delay filling clopidogrel.

3. Explain the purpose of the interview

I/we are interviewing a number of people at your site who can help us understand the medication and hospital discharge process for PCI patients, and how this project might best fit in with what is going on now. We wanted to talk with you before the Hybrid Effectiveness-Implementation Clopidogrel Study is implemented so we can understand what is going on now to improve clopidogrel adherence, how you currently work with primary care, and hear your opinions about how the study should work here.

4. Describe how we will assure confidentiality, obtain consent, and answer any questions.

I want to let you know what will happen to the information you provide. I am recording this conversation so that we do not miss anything that you have to say. People working on this study will be the only ones who will use the interview recordings and the recordings will be stored on the secure VA site behind VA firewall. We will take steps to ensure the information you provide remains confidential. Individuals will not be named in any notes, report or summary.

1. Role of interviewee

1.1. I'd like to begin by asking what your role is within this facility.

1.2. Probes:

1.2.1. Do you have responsibilities outside this facility?

1.2.2. Is there anything else?

2. Current discharge medication process
 - 2.1. Can you give me a brief overview of how discharge medication is organized here?
 - 2.2. Probes:
 - 2.2.1. When do patients receive discharge medications?
 - 2.3. When and how do you provide education to the patient or their caregivers about medications?
 - 2.4. When and how is communication with the patients' primary care team handled?
3. Current challenges to discharge medication process
 - 3.1. What challenges do you (or your facility) see in ensuring that PCI patients are discharged on clopidogrel?
 - 3.2. What challenges do you (or your facility) see in ensuring that hospital patients in general are discharged on required medications?
 - 3.3. Probes:
 - 3.3.1. What are the main things that contribute to these challenges?
 - 3.3.2. Main Facilitators?
4. Current challenges to clopidogrel adherence in the outpatient setting
 - 4.1. Do you think patient are taking clopidogrel as prescribed in the outpatient setting?
 - 4.2. What challenges do you (or your facility) see in ensuring that patients refill and continue to take clopidogrel as prescribed?
 - 4.3. Probes:
 - 4.3.1. What are the main things that contribute difficulties with adhering to clopidogrel treatment?
 - 4.3.2. What do you think are things that can help patients take clopidogrel as prescribed?
5. Receptiveness to Hybrid Effectiveness-Implementation Clopidogrel Study Intervention
 - 5.1. How receptive do you think clinicians [and others] will be to the intervention? Why?
 - 5.2. What concerns do you think pharmacists and clinicians might have about this intervention? How do you think we could address these concerns?
 - 5.3. What other changes would you recommend to make the intervention more effective? Easier to implement?
 - 5.4. How big of a change do you think the intervention will be compared to the way you're currently managing clopidogrel prescriptions for hospital patients?
6. Clinician views of intervention
 - 6.1. When you imagine actually implementing an intervention like this, what kinds of things would cause you to be enthusiastic about it?
 - 6.2. What kinds of things would cause you to be uncomfortable about an intervention like this?
7. The Environment
 - 7.1. On a scale of 0 to 10, how difficult would it be to implement this program in this facility? Why?
 - 7.2. On a scale of 0 to 10, how much do you think the program will help patients? Why?
 - 7.3. What kind of feedback would you want about the program when it is implemented (e.g., # pts eligible, clopidogrel adherence rate, stories from patients)?
 - 7.4. What can we do to help staff feel prepared and confident about the intervention?

8. Sustainability

- 8.1. What else are the most important things that we would need to show for this facility to continue/expand a program like Hybrid Effectiveness-Implementation Clopidogrel Study?
- 8.2. What kind of case would need to be made to convince people to continue/expand this program after the evaluation phase is done?
- 8.3. Do you have any recommendations or considerations that we haven't discussed?
- 8.4. Anything you'd like to suggest as we refine the intervention over the next few months?

9. Close

That covers all the questions that we wanted to ask. Thank you so much for all the information you have provided.

- 9.1. Do you have any final questions for us?
- 9.2. Is it ok if we contact you for another interview in the future?

Appendix 3: Interviews to assess barriers and facilitators to intervention implementation of clopidogrel adherence programs

Provider/Intervention Personnel Questions:

1. What is your current role in the Hybrid effectiveness-implementation clopidogrel study?
2. Please tell us about your experience with the Hybrid effectiveness-implementation clopidogrel study to date.
3. What's your impression of how it's going (questions for inpatient pharmacist or other designee for education and bring clopidogrel to the bedside)?
 - a. Are you being notified that a PCI procedure has been performed?
 - b. If not, why?
 - c. How can the notification process be improved?
 - d. Do you have time to educate and bring clopidogrel to the patient's bedside?
 - e. If not, what are the barriers?
 - f. How can the education process or the process of bring clopidogrel to the bedside be improved?
 - g. Other suggestions to improving the discharge process for patients receiving a stent?
4. What's your impression of how it's going (questions for outpatient PACT team member or other designee)?
 - a. Have you been notified that a patient has not refilled clopidogrel?
 - b. If yes, did you contact the patient and what did you do when you contacted the patient?
 - c. How do you think the process can be improved?
5. Scale of 0 to 10, how difficult has it been to implement this program at your facility? Why?
6. What should be modified or improved?

Patient Questions:

1. Please tell us about your experience with the Hybrid effectiveness-implementation clopidogrel study to date.
2. What's your impression of the discharge process?
 - a. Did you receive any education about clopidogrel prior to discharge? If so, what did you think of the education that you received?
 - b. Did you receive the clopidogrel wallet card prior to discharge? If so, what did you think of the wallet card that you received and do you carry it with you?
 - c. Did someone bring clopidogrel to the bedside prior to discharge? If so, what did you think of that?
3. Have you received an automated call reminding you to refill your clopidogrel?
 - a. If yes, what did you think of the call? Was it helpful in reminding you to refill your medication?
 - b. If not, what would make it more helpful to remind you to refill your medication?
 - c. Did you use other options on the IVR call such as being connected to the pharmacy refill line or having the pharmacist call you to answer your questions?
 - d. If yes, how was the process of interacting with the telephone system?
 - e. What other features would you like to see with the telephone system?
4. Scale of 0 to 10, how much is a program like this helping you? Why?

Hybrid Effectiveness-Implementation Study to Improve Clopidogrel Adherence

NCT01609842

ADDENDUM TO STATISTICAL ANALYSIS PLAN

Document Date: May 1, 2019

Uploaded: 05/06/2019

We have made the following additions and clarifications to the original Statistical Analysis plan (described in the study protocol):

- 1. In addition to the intervention group of patients who were treated during the 6 month intervention period, we consider three control groups: a) patients who were treated at a site before the intervention was applied there, b) patients who were treated at a site after the intervention was ended there, and c) patients who were treated at a site that was eligible but at which the intervention was never applied. The primary hypothesis is intervention versus pre-intervention, and other comparisons are considered secondary analyses.
- 2. We used mixed logistic regression models for clopidogrel adherence (y/n PDC > 80%) as planned. To express results on a more interpretable risk difference scale we used standardized or average predicted value estimators (e.g. Zou, 2009; Joffe and Greenland, 1995), which compare probabilities of adherence among the groups, hypothesizing (in some cases counterfactually) that patients were in each of the four intervention/control groups. Inference was carried out using bootstrap methods and results expressed as confidence intervals for differences between groups. The same methods were used to express survival probabilities and differences in more interpretable terms (Sjolander, 2016).
- 3. Sensitivity analyses were carried out removing patients who received bare metal stents.

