Therefore, our main objective is to conduct a type 1 hybrid effectiveness/implementation study to test the effectiveness of a successfully-piloted, evidence-based, multi-faceted intervention to improve patient adherence to clopidogrel following PCI. The proposed study will test the hypothesis that a successfully-piloted, evidence-based, multi-faceted intervention targeting veterans following PCI procedure improves adherence to clopidogrel, reduces bleeding, myocardial infarction, stroke, and mortality among these patients, and is cost-effective. The proposed intervention will be based on the Chronic Care Model and will build on our pilot work as well as will leverage the VA's CART-CL, a uniform cath lab procedure reporting tool at all VA cath labs. The study will be evaluated using the RE-AIM framework consisting of the following components, reach, effectiveness, adoption, implementation and maintenance. The intervention will adapt elements of prior successful intervention, including patient education, collaboration between cath lab clinicians and inpatient/outpatient pharmacy teams, and tele-monitoring via interactive voice response (IVR) technology. This type I hybrid effectiveness/implementation study will be tested at 16 sites randomized to intervention with an average of 90 patients per site per 6 month period versus usual care.

Specific Aims:

1. To evaluate current practices at VA PCI facilities (n=16) to enhance adherence to clopidogrel, both at hospital discharge and during longitudinal follow-up.
2. To implement the multi-faceted intervention at 16 total sites through 4 roll-out phases (4 sites during each roll-out) in a randomized stepped wedge trial design.

3. To assess barriers and facilitators to intervention implementation during each roll-out phase through semi-structured interviews and incorporate lessons learned from each roll-out phase into subsequent roll-out phases.
4. To determine the effectiveness of a successfully-piloted, evidence-based, multi-faceted intervention versus usual care for improving clopidogrel filling at hospital discharge and adherence to clopidogrel (primary outcomes).
5. To determine the effectiveness of a successfully-piloted, evidence-based, multi-faceted intervention versus usual care for reducing the combined cardiovascular endpoints of bleeding, myocardial infarction, stroke, and mortality (secondary outcomes).

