6. To assess the incremental cost-effectiveness of the successfully-piloted, evidence-based, multi-faceted intervention compared with usual care.

II. Background and Significance:

PCI is a common invasive cardiovascular procedure performed in the VA with over 13,000 procedures in FY10. Clopidogrel is a critical adjuvant therapy following PCI with stent placement and is generally recommended for up to 1 year following the procedure (1). This is a class I recommendation in the American College of Cardiology (ACC)/American Heart Association (AHA) guidelines, which is the highest level of recommendation in the guidelines (1). Despite the evidence supporting clopidogrel use, studies both outside and within the VA suggest that poor adherence to clopidogrel is common. However, prior interventions targeting non-adherence have not specifically focused on clopidogrel adherence among PCI patients.

Non-adherence to clopidogrel among PCI patients is common in the VA. From CART, we found that 22.4% of patients delayed filling clopidogrel following PCI in FY09 with delay defined as filling a clopidogrel prescription > 1 day after discharge. Further, approximately 1/3 of patients discontinued clopidogrel early (< 9 months) prior to the recommended one year treatment duration. Even among patients without an initial delay in clopidogrel filling, almost 40% of patients discontinued clopidogrel by 9 months of hospital discharge. At the hospital level, there is also significant variation in clopidogrel non-adherence. On average at each PCI facility, 18.9% of patients delay filling clopidogrel, and 30-40% discontinue clopidogrel early by 9 months. These findings highlight significant opportunities to improve clopidogrel adherence following stent implantation in the VA.

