At the PCI sites, we will include all patients undergoing PCI with either a bare-metal (BMS) or drug-eluting stent (DES) and are prescribed clopidogrel regardless of the intended treatment duration. We will include other potential anti-platelet medications (thienopyridines) used following PCI to accommodate changes in practice (e.g., prasugrel or ticagrelor or ticlopidine). Based on FY10, there were >10,000 patients undergoing PCI with either a BMS or DES at these facilities.

We will include all patients undergoing PCI and receiving clopidogrel at the randomized sites, regardless of gender, ethnicity or race. Based on data from the national CART Program, we anticipate ~23% minorities (African American 16.8%, Hispanic 4.4%, Asian/American Indian 1.4%) and 3.1% women will be included in the study.

C. Study Design and Research Methods:

We are proposing a type I hybrid effectiveness-implementation study of a multi-faceted intervention to improve clopidogrel adherence at VA PCI centers.

An overview of the number of patients and providers involved with interviews and the recruitment process is defined below:

Aim 1 – Identified sites will be stratified into quintiles and randomized to either the intervention or the control arm. We will choose approximately any 3 sites randomized to the intervention to be purposively sampled. We will interview up to 12 providers at each site. The interviews will be used to modify the

email survey that will be sent to all 16 sites targeting key personnel described in detail later in the protocol. After the survey results have been evaluated we will follow up with approximately 2-3 additional qualitative interviews based on results from the survey. A single provider may be interviewed more than once if they happened to have identified specific local barriers or facilitators in their survey responses. Therefore, we plan on collecting up to 96 telephone interviews from the 16 intervention sites. In addition, we will conduct site visits at approximately 2-3 of the 16 intervention sites. During these visits, we will interview up to 10 providers at each site.

Aim 2 – The implementation of the intervention will involve recruiting up to 2,500 patients at 16 sites.

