We will employ well-developed and well-tested data management procedures to ensure accurate and efficient data collection and analysis, as we have done for our prior/current IVR projects and in several other IHD-QUERI studies. Some CART data for this study will be pulled from the database established under 06-1149. Different elements of the proposed study database system are in current use (e.g., hypertension IVR [Improving Blood Pressure in Colorado]; and MEDICATION [IIR 08-302]), and are easily adaptable to the current proposal (i.e. this study deals with a different aspect of cardiovascular disease). There are internal error checks (e.g. detection of pre-specified out-of-range data values and incorrect skip patterns), data definitions, and missing data checks. As part of the database, pharmacists will have the ability to document that education was provided to the patient, that clopidogrel was brought to the patient's bedside prior to hospital discharge, and to confirm phone numbers that the patient can be reached at. The system will also allow for tracking of number of patients enrolled per site based on the PCI procedures inputted into CART-CL.

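### Does the primary contrast compare enrolled intervention patients with all pre-intervention patients?

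*SAP*

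**What the plan says.** Addendum item 1 sets out an intervention group, "the intervention group of patients who were treated during the 6 month intervention period", and three control groups: patients treated at a site before the intervention, patients treated there after it ended, and "patients who were treated at a site that was eligible but at which the intervention was never applied". It then ranks the comparisons: "The primary hypothesis is intervention versus pre-intervention, and other comparisons are considered secondary analyses". Enrolment, consent and opt-out are not mentioned.

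The protocol has two strands on who is in the study.

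- **Population and data.** Section IV.B states: "We will include all patients undergoing PCI and receiving clopidogrel at the randomized sites, regardless of gender, ethnicity or race". The same section, and Randomization Process under Aim 2, have outcomes collected centrally from national VA sources for both arms. Section IV.D adds: "The system will also allow for tracking of number of patients enrolled per site based on the PCI procedures inputted into CART-CL". Section I plans for "an average of 90 patients per site per 6 month period".
- **Recruitment and delivery.** Sections IV (Overview) and IV.B speak of enrolling patients over 6 months, with a possible extra month where enrolment goals are missed. Section IV.C gives a ceiling of 2,500 recruited at 16 sites. Intervention Components under Aim 2 describes verbal consent, refusal or later opt-out, a master list of participants, and enrolment completed by telephone when no study staff are on hand.

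Neither document has a sentence headed as an analysis set, and neither says how a refuser or an unreached patient is counted.

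**The concern.** Consent and contact are described only for intervention sites in their intervention window. Pre-intervention data are fill and adherence records at each site (section IV.F). That these patients pass no enrolment step is an inference, but nothing in the documents suggests otherwise.

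An enrolled-only intervention group would therefore be filtered on agreeing and being reachable, and its comparator would not. Both traits may go with better adherence. The model terms for site, roll-out period and stratum cannot remove selection between patients within a site. Filling at discharge is exposed too: bedside delivery normally happens at the same visit as consent, so restricting to enrolled patients could raise the fill rate partly by construction.

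A smaller worry concerns the third control group. Recruitment under Aim 2 calls 66 sites eligible for randomization, while section IV.B says the 14 sites in the lowest quintile are never randomized. Read literally, the group could have 50 or 36 sites, and the place of sites that were drawn but declined is not stated.

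**Working it through.** **1. The plan's own site count.** Four upper quintiles of 13 sites: 4 × 13 = 52. Less 16 intervention sites: 52 − 16 = 36, as stated. Adding the 14 lowest-quintile sites: 52 + 14 = 66, also as stated. The 50-site reading is 66 − 16. It needs the one word *eligible* to override the figure of 36, which is given in section IV.B and, under Aim 2, in both Study design and Randomization Process. The only stated role of the lowest quintile is to supply interviews (Aim 1, steps 4 and 5).

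**2. Planned patient numbers.** Intervention: 16 × 90 = 1,440. Pre-intervention, with one baseline period and four roll-out periods: the four cohorts contribute 1, 2, 3 and 4 untreated periods at 4 sites each, so 4 × (1 + 2 + 3 + 4) = 40 site-periods and 40 × 90 = 3,600 patients. The 2,500 ceiling is 2,500/16 = 156 per site; being an upper limit, it does not conflict with 1,440.

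**3. Does 90 per site show which group is meant?** Two FY10 figures bracket the flow: "there were >10,000 patients undergoing PCI with either a BMS or DES at these facilities" (a lower bound, stented patients) and "over 13,000 procedures in FY10" (all PCI, so too high for stents). Spreading both over 66 sites is an assumption.

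- 10,000/66/2 = 75.8 per site per half-year; 90/75.8 = 1.19
- 13,000/66/2 = 98.5 per site per half-year; 90/98.5 = 0.91

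The planned number is about the whole eligible flow. That fits counting everyone, but it is weak evidence: intervention sites come only from four quintiles, and the exclusion of patients not discharged home is not applied.

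**4. Size of the bias if the analysis were enrolled-only.** Let s be the share of eligible patients not enrolled and g the adherence gap, enrolled minus not enrolled. With no true effect, bias = s × g. Both inputs, and the direction of g, are assumptions.

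| s | g = 10 points | g = 20 points |
|---|---|---|
| 0 | 0 | 0 |
| 10% | 1 | 2 |
| 20% | 2 | 4 |
| 30% | 3 | 6 |

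**5. Yardstick.** Linear model on 52 sites × 5 periods, 90 patients per cell, cell variance p(1 − p)/90, fixed site and period terms plus intervention and post-intervention terms. The 95% half-width of the primary contrast, in percentage points:

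| | p = 0.50 | p = 0.65 | p = 0.80 |
|---|---|---|---|
| 36 control sites | 3.3 | 3.1 | 2.6 |
| No control sites | 4.2 | 4.0 | 3.4 |
| 36 controls, assumed site-by-period SD of 3 points | 3.8 | 3.6 | 3.2 |
| 36 controls, assumed site-by-period SD of 5 points | 4.5 | 4.4 | 4.0 |

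A bias of 2–4 points would be of the same order as the best-case half-width, so an enrolled-only primary analysis would matter. Whether the plan calls for one has to be read from the text.

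**6. Passages side by side.** The addendum uses the same treated-at-a-site definition for all four groups. Section IV.B includes all eligible patients at the randomized sites. Outcomes are drawn from records for both arms, so a refuser's outcome would not be lost for want of contact. Section IV.D counts enrolment from CART-CL procedures. Against this, the consent, opt-out and telephone passages say how the intervention reaches a patient, and the enrolment and recruitment passages say how long and how many. None of them limits the analysis to enrolled patients.

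**The case for a change.** The strongest case for a change is that a primary analysis set should not have to be inferred. The protocol repeatedly uses the language of an enrolled cohort, and even the sentence in section IV.D counts enrolled patients from procedures, which blurs the two ideas. The addendum is written in the past tense, so the sponsor already knows which patients were analysed and could say so at almost no cost. If the analysis was in fact enrolled-only, a rerun on centrally held data would be warranted.

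Part of this stands. The documents are silent on refusers, opt-outs and unreached patients, and a sentence naming the group would help a reader. But the silence is a missing detail beside operative text that points one way, and an enrolled-only analysis is possible without being shown. The bias figures rest wholly on assumed inputs and treat the raw gap as the bias. Sections IV.D and IV.E provide for patient covariates and for multivariable models where groups are imbalanced, and addendum item 2 standardises over the model, so some of any gap could be absorbed. The yardstick also sets site-by-period variance to zero; allowing for it widens the interval to 3.2–4.5 points, against which the same bias looks smaller.

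On the third control group, removing sites that declined would sit badly with keeping patients who refused. The addendum's literal wording admits declining sites, and no bias from them has been shown.

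**Conclusion.** The concern does not call for a change. Taken as written, the addendum and section IV.B give a comparison of all eligible treated patients in both periods, and the enrolment-selection bias in that comparison is zero. The 1–6 point range applies only to an analysis that the documents do not describe, and it depends on an assumed non-enrolment share, an assumed adherence gap and an assumed direction. The missing statement about refusers and unreached patients is a gap that an analyst using the central records would fill sensibly by applying the same eligibility filters to both periods. Information on reach is also provided for: the protocol plans a RE-AIM evaluation, a participant list with documented opt-outs, and tracking of enrolment per site.

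The site question does not alter this. The control count reproduces at 36, and the ambiguity mainly touches a secondary comparison. Control sites do inform the primary contrast through the shared period terms (half-width 2.6–3.3 points with them, 3.4–4.2 without), but no bias from their definition can be derived from the documents.

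The conclusion rests on reading *treated* in its ordinary sense. It would be different if the completed analysis turned out to be limited to enrolled patients.
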